### **7.3.5      Interim analyses**

No interim analysis is planned for this study.

### **7.4            HANDLING OF MISSING DATA**

In general, no specific method of handling missing data is foreseen for this study. The analyses will be performed on all available data.

However, for the primary endpoint, a sensitivity analysis with missing data handling should be planned and detailed in the Statistical Analysis Plan (SAP) before database lock.

### **7.5            RANDOMISATION**

Patients will be randomised in one of the 2 study groups following a ratio of 3:1 (3 patients in the with 'remote additional personalised nurse-led follow-up' group for each one patient in the without 'remote additional personalised nurse-led follow-up'), and according to a list of randomisation previously defined.

This list will be generated before the start of the study according to all the following criteria:

- Blocks of different size: 4 and 8.
- Parallel groups.
- Including 2 treatment groups.
- Following a 3:1 ratio.

It will be implemented using a validated computer tool which allows generating a sequence of pseudo-random numbers and selecting of a number called 'seed randomisation', not communicated to operational involved in the project, to ensure the non-reproducibility and non-predictability of the generation of randomisation list.

The allocation of a patient to one study group or the other ('with remote additional personalised nurse-led follow-up' versus 'without remote additional personalised nurse-led follow-up' will be done sequentially within each centre using randomisation envelope. To limit selection bias in the absence of central randomisation, the blocks of randomisation will be of varying size (4 or 8).

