##### **Study design:**

The study will take place over a period of 27 months. The recruitment phase will last approximately 24 months and each patient will participate for approximately 3 months.

At the inclusion visit (D0), the investigator will ask the patient whether he would like to participate in the study and will obtain his written consent. Refusal to participate including the reason if available will be collected in a register specific to this study (study register). The collected data will allow any selection bias to be identified.

Each patient agreeing to participate in the study will be randomised by receiving a randomisation number and assigned to its corresponding group. Randomisation will be done by envelopes (See Section 7.5). The investigators or medical team will send a randomisation fax to Patientys for each patient included in the study. Patientys will forward the anonymised data to the contract research organisation (CRO) in charge of the data monitoring.

The randomisation will follow a 3:1 ratio and the patients will be included in one of the following 2 groups:

- Group without 'remote additional personalised nurse-led follow-up': patients will receive the healthcare given routinely by their medical team (100 patients).

OR

- Group with 'remote additional personalised nurse-led follow-up': patients will receive telephone calls from a nurse in addition to the healthcare given routinely by their medical team (300 patients).

All the patients will be seen according to normal practice by the study medical team. In this study, 3 data collection time-points at monthly intervals are defined (D30, D60, D90); however the frequency of visits should not be adjusted and the medical team should maintain his routine practice (example: if the investigator is used to see the patient on D15, the visit will still take place, but no information, except pharmacovigilance data, will be collected). As

such, the data from the closest defined visit will be reported in the case report form (CRF) at each time point (see Figure 1).

During the inclusion consultation, the medical team will provide the patient with a patient diary with all the main information regarding its treatment and in which he should report some information (see Section 6.2).

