## 7. STATISTICAL METHODS AND DETERMINATION OF PATIENTS SAMPLE SIZE

### 7.1 STATISTICAL DESIGN

This is a routine clinical practice, randomised, open-label, multicentre, study.

Patients will be randomised in one of the following 2 groups:

- Group ‘without remote additional personalised nurse-led follow-up’: patients will receive the healthcare given routinely by the medical team (100 patients).
- Group with ‘remote additional personalised nurse-led follow-up’: patients will receive telephone calls from a nurse in addition to the healthcare given routinely by their medical team (300 patients).

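### Section 7.5 relies on varying block size to limit selection bias but prints both sizes in the protocol, which weakens the safeguard without removing it

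*Combined protocol and SAP*

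**What the plan says.** Section 7.5 (Randomisation) lists the properties of the allocation list, among them "Blocks of different size: 4 and 8". It says that allocation "will be done sequentially within each centre using randomisation envelope". It then explains why the block size varies: "To limit selection bias in the absence of central randomisation, the blocks of randomisation will be of varying size (4 or 8". The same section withholds the seed from operational staff so that the list cannot be predicted. It does not say that the block sizes are withheld from sites.

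Section 7.1 states: "This is a routine clinical practice, randomised, open-label, multicentre, study". The team therefore learns each arm once it is assigned. Section 3.1 also specifies envelopes, plans 130 medical teams in 75 centres with about 5 to 6 patients each, and adds: "The investigators or medical team will send a randomisation fax to Patientys for each patient included in the study". Section 6.2.1 has a registration form sent to Patientys by e-mail or fax. No section says that the envelopes are sealed, opaque or numbered, when they are opened relative to registration, or that their use is logged.

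**The concern.** Varying block size is the only measure that Section 7.5 offers in place of central randomisation. Printing both sizes in the document from which investigators work gives away part of it: anyone who knows the sizes and the centre's past allocations can update the odds for the next patient.

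Those odds could be acted on. Eligibility includes the investigator's opinion that the patient is able to participate (Section 3.3.2), and invitation, consent and randomisation all take place at D0. An investigator could withhold or delay an invitation. The study register described in Sections 3.1 and 6.2.1 records patients who refuse; nothing provides for recording eligible patients who were never invited, so such selection would not show. The primary analysis in Section 7.3.2 is a Student or Wilcoxon comparison without centre or baseline covariates, so an imbalance produced this way would pass into the estimated dose difference.

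**Working it through.** **Inputs.** Block sizes 4 and 8, ratio 3:1, sequential allocation within centre (Section 7.5); open-label (Section 7.1); about 5 to 6 patients per centre (Section 3.1). Two assumptions are needed. First, the documents do not give the mix of sizes, so the base case takes 4 and 8 as equally likely at each new block, with all 4s and all 8s as the range. Second, each centre starts its own block, which the sequential within-centre wording implies but does not state. N is nurse arm, C is control.

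**The plan's own figure.** Section 3.2 gives each patient a probability of 0.75 of the nurse arm. Both block sizes reproduce it: 3/4 = 6/8 = 0.75, so the nominal P(C) is 25%.

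**After a first control.** A first C is equally likely under either size, so the sizes remain 50/50. A block of 4 has no C left (0/3); a block of 8 has one in seven.
P(C | C) = ½ × 0 + ½ × 1/7 = 1/14 = 7.1%. All 4s: 0%. All 8s: 14.3%.

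**After three nurse allocations.**
P(NNN | block of 4) = 1/4. P(NNN | block of 8) = 6/8 × 5/7 × 4/6 = 5/14.
P(NNN) = ½ × (1/4 + 5/14) = 17/56 = 30.4%.
P(block of 4 | NNN) = (1/4) / (1/4 + 5/14) = 7/17.
P(C | NNN) = 7/17 × 1 + 10/17 × 2/5 = 11/17 = 64.7%. All 4s: 100%. All 8s: 2/5 = 40%.

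**Exact enumeration over the first six patients, equal mix.** Each cell is the percentage of allocations at that position.

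| Patient | P(C) below 15% | P(C) above 50% | Certain | Best guess right |
|---|---|---|---|---|
| 1 | 0 | 0 | 0 | 75.0 |
| 2 | 25.0 | 0 | 0 | 75.0 |
| 3 | 48.2 | 0 | 1.8 | 75.0 |
| 4 | 69.6 | 30.4 | 5.4 | 83.9 |
| 5 | 10.7 | 0 | 10.7 | 75.0 |
| 6 | 30.4 | 5.4 | 10.7 | 76.8 |
| Mean | 30.7 | 6.0 | 4.8 | 76.8 |

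After NNNN, P(C) is exactly 50%. Counting that case gives 7.7% at or above 50%, against 6.0% strictly above.

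**Range over the unstated mix (means over six patients).**

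| | Equal mix | All 8s | All 4s |
|---|---|---|---|
| P(C) below 15% | 31% | 16% | 29% |
| P(C) above 50% | 6.0% | 1.8% | 4.2% |
| Certain | 4.8% | 12% | 33% |
| Best guess right | 76.8% | 75.6% | 79.2% |

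In the equal mix, every certain allocation within six patients is to the nurse arm; none is a certain control.

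**The case against.** The strongest reply is that the practical exposure is small. Always guessing the nurse arm is already right 75% of the time, and knowing the block sizes raises that only to 76.8%. The 64.7% case needs three nurse allocations first, which happens in 30.4% of centres, and then a fourth patient. With 400/130, about 3 patients per team over some 24 months, there is rarely a queue to reorder, and a team that shares a centre must know its colleagues' allocations. Consent already precedes randomisation (Section 8.1). No document shows that anyone has a motive to steer.

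Most of this stands, and it sets the size of the point. It does not remove it. The average hides the conditional odds, and those are what selection would use: about three allocations in ten are known to have less than a 15% chance of control. Infrequent recruitment weakens the opportunity to time invitations, but not the opportunity to withhold one.

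Two stronger readings are tempting. A reader might infer that varying sizes are useless once known. They are not: certain allocations are 4.8% in the equal mix against 33% with fixed blocks of 4. A reader might also infer from the 4.8% that investigators can foresee control patients with certainty. Within six patients in the equal mix, they never can.

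**Conclusion.** The point holds as a weakness in allocation concealment that is cheap to correct. Section 7.5 discloses the feature it relies on, in an open-label study with small centres and no described control over the opening of envelopes. The chance of control can move from 25% to 64.7% (40% to 100% over the mixes) or to 7.1% (0% to 14.3%), and 31% of a centre's first six allocations (16% to 31%) have it below 15%.

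These figures assume the block mix stated above, a separate block start in each centre, and full knowledge of the centre's past allocations. A reader might go further and conclude that the primary dose comparison is biased. The documents do not support that: they do not show that any investigator would act on the odds, and they give no basis for a bias in mg to set against the 180 mg planned difference (3180 − 3000, Section 7.6). Selection could bias the comparison; that it does has not been shown.

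**What to change.** Delete both mentions of the block sizes from Section 7.5. Regenerate the list with new, undisclosed sizes and hold them in a restricted randomisation document. A 3:1 ratio still requires multiples of four, so this reduces predictability rather than abolishing it.

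Keep envelopes, but state that they are sealed, opaque and sequentially numbered. They should be opened only after signed consent and after the patient has been registered on the existing fax or e-mail form, with envelope number, date and time logged.

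The cost is protocol wording, a regenerated list, a log, and sending the registration form before the envelope is opened. The documents do not say whether that form and the randomisation fax of Section 3.1 are one document; if they are, the arm must follow in a second message.

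Central release of the allocation would be stronger, but it is optional and not part of the cheap fix. The fax is described only as going from site to Patientys, the CRO hotline has no stated randomisation role, and a staffed reply service would be new. If it is adopted, it should not sit with Patientys, which makes the nurse calls.

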## **7.6 DETERMINATION OF SAMPLE SIZE**

In the absence of dose discontinuation or reduction, the cumulated dose of oral targeted therapy should be 3600 mg of afatinib, which corresponds to a daily dose of 40 mg for 90 days.

Clinical trials performed with afatinib before its marketing authorisation showed that over the first 3-month follow-up the mean dose of 3000 mg was taken (which corresponds to a dose intensity of 83%) (Boehringer Ingelheim First Interim Study Report 1200.32).

It was estimated that the mean dose observed in the group ‘without remote additional personalised nurse-led follow-up’ will be similar to the mean dose observed in the afatinib clinical trials and that adding an additional nurse-led follow-up will increase the mean dose by 6% (3180 mg, dose intensity of 88%).

As such, the number of patients to be included in the study has been calculated on the basis of a t-test for 2 unmatched samples with the following hypotheses:

- Mean cumulated dose of oral targeted therapy taken during the 3-month follow-up in the group ‘without remote additional personalised nurse-led follow-up’: 3000 mg (dose intensity of 83%).
- Mean cumulated dose of oral targeted therapy taken during the 3-month study in the group ‘with remote additional personalised nurse-led follow-up’: 3180 mg (dose intensity of 88%).
- Standard deviation of the cumulated dose of oral targeted therapy taken during the 3-month follow-up in both groups: 500.
- Type I error:  $\alpha = 0.05$ .
- Type II error:  $\beta = 0.20$  (power = 80%).
- Ratio ‘with remote additional personalised nurse-led follow-up’ group/‘without remote additional personalised nurse-led follow-up’ group = 3.

Using these hypotheses, in order to show an increase in the cumulated dose with the addition of 3-month nurse-led follow-up, it is necessary to have 82 patients in the group ‘without remote additional personalised nurse-led follow-up’ and 246 patients in the group ‘with remote additional personalised nurse-led follow-up’.

If it is considered that 20% of included patients will be non-evaluable for the primary criterion, it is necessary to include 99 patients in the group ‘without remote additional personalised nurse-led follow-up’ and 297 patients in the group ‘with remote additional personalised nurse-led follow-up’, i.e. 396 patients in total which can be rounded up to 400.

## **8. INFORMED CONSENT, DATA PROTECTION, STUDY RECORDS**

This study will be conducted according to the protocol, following the principles of Helsinki Declaration, GCPs requirements (transposition into French law of "ICH-GCP" [International Conference of Harmonization-Good Clinical Practice]) and the applicable legislation, and according to standard procedures of Boehringer Ingelheim. Routine medical care remains the responsibility of the general practitioner of the patient.

The medical team must immediately inform the sponsor or his representative of any emergency measures taken to protect patients from immediate danger, in addition to any violation of the protocol and GCPs.

### **Insurance:**

This study is a clinical routine practice study and, in accordance with the law, is covered by the liability insurance of the participants in the study centres.

### **8.1 STUDY APPROVAL, PATIENT INFORMATION, AND INFORMED CONSENT**

This study will be initiated once all documents are reviewed by ethics committee (Comité de Protection des Personnes [CPP] Ile de France II) and other relevant health institutions concerned with studies of routine practice in accordance with applicable French legislation (Comité Consultatif sur le Traitement de l'Information en matière de Recherche dans le domaine de la santé [CCTRIS] / Commission Nationale de l'Informatique et des Libertés [CNIL], Conseil National de l'Ordre National des Médecins [CNOM]). Any substantial change to the protocol will be implemented only after receiving the approval of the CPP. Non-substantial changes will be informed to the CPP.

Patients participating in a routine practice study should be informed of the purpose of the study, duration, number of participants and their right to refuse participation in the study. Patients will be verbally informed by the medical team and will receive a copy of the patient information consent form (Appendix 10.1) which they must sign. This written consent must be obtained prior to initiation of any procedure related to the study.

The data collected during this study will be processed by computer. Treatment may be carried out in France or abroad, and will be conducted in compliance with the French law n° 78-17 of 6 January 1978 relating to computers, files and freedoms, as amended by Law 2004-801 of August 6, 2004. All necessary measures to ensure data confidentiality will be taken in accordance with the applicable legislation. Patients will not be identified by name or date of birth on the case report form or any other study document submitted to the sponsor or his representative. Patients will receive a unique identification number upon their consent to participate in the study. Patients should be informed that their medical records may be reviewed by staff appointed by the sponsor or his representative or by inspectors from the related authorities.

## **8.2        QUALITY CONTROL**

Investigators have the responsibility to collect and report data in the CRF. It shall ensure that data are fully and accurately reported and are consistent with the source data.

An audit or inspection of this study can be made by the sponsor or any of [redacted] representatives, or by relevant authorities to ensure that the study is being conducted according to GCP and applicable legislation.

## **8.3        RECORDS MANAGEMENT**

### **8.3.1      Data management**

All information required by the protocol will be recorded on paper CRFs which will be completed by the medical teams as well as on the self-administered questionnaires completed by patients.

The CRFs and questionnaires will be sent by the medical team to the CRO in charge of data monitoring by postal mail as soon as the patient has completed the study. The nurses in the call centre specialised in following-up patients will also send, weekly, a copy of the AEs page of to the CRO in charge of data monitoring.

A study-specific database will be created, tested and validated prior to data entry. Data entry will be performed by the team responsible for managing the duplicate data entry. A plan for data validation will be developed and will describe, in details, the controls run for each variable as well as the list of corrections that are obvious and authorized.

The integrity of the case report forms will be checked upon receipt and then will be used for data entry. The data will then be controlled by the team responsible for data management, by using the error messages from the validation programs. Obvious errors will be corrected. Other errors, omissions or inconsistencies, will be mentioned on query forms that will be sent to the investigator for correction (this measure concerns only the CRF of doctors and is not applicable to patient self-report questionnaires). After receiving the query forms completed by the investigator, corrections will be included in the database.

The database will be locked after a final quality control and finalisation of the SAP.

### **8.3.2      Source documents**

CRF will be provided for each patient. Predefined questionnaires will be given to Patients' nurses to use for data collection during the telephone call. Patients should complete the self-administered questionnaires as specified in the protocol. All these documents are considered the source documents of the study.

Data on patient demographics and their medical history will be collected from the patient's medical record (See Section 6.2).

### **8.3.3 Access to source documents**

The investigator or study centre will authorise audit visits and review of data by auditors or inspectors. CRFs and any other source documents, including study notes and copies of medical examination must be available upon request for review by the sponsor or auditors.

### **8.3.4 Storage of records**

#### Investigators

Documents related to this study will be archived in accordance with GCP for a period of 15 years after the end of the study. Medical teams and the sponsor should archive documents related to the study in accordance with the applicable regulations.

Any change in the arrangements for archiving or any document destruction cannot be done without the consent of the sponsor. After the archival life, the sponsor will be consulted for the disposal terms and will have to agree in writing.

[figure not shown]
## **8.4 NOTIFICATION OF ADVERSE EVENTS AND OTHERS PHARMACOVIGILANCE INFORMATIONS**

SAEs must be immediately reported to the CRO in charge of data monitoring (within 24h following the knowledge of the event) and forwarded by the CRO to the sponsor pharmacovigilance department on the same day. Non-serious AEs and any other PV information must be reported to the CRO in charge of the data monitoring within 7 days of knowledge and forwarded to the sponsor pharmacovigilance department within the next 7 days (Figure 2).

The Patientys call centre nurses will send information related to AE and other PV information to the investigator of the medical team via the telephone call report (█ is responsible to assess the intensity and the causal relationship) on the day of the phone call.

- In case of SAE: the investigator must immediately send the completed SAE form to the CRO in charge of the data monitoring (within 24h of knowledge). The CRO must inform the sponsor's PV department and forward the SAE form on same day.
- In case of non-serious AE or of any other PV information: the investigator must complete and send the AEs page of the CRF to the CRO in charge of the data monitoring within 7 calendar days following the event. The CRO will establish a list of non-serious AEs related to the oral targeted therapy and will provide it to the sponsor weekly.

**Figure 2      Procedure for reporting serious and non-serious adverse events**

The telephone call report contains the AE page(s) of the CRF and the SAE form(s)  
TCR = telephone call report, AE= adverse event, SAE = serious adverse event, CRF = case report form, CRO = contract research organization.

## **8.5 STATEMENT OF CONFIDENTIALITY**

Individual medical information of each patient obtained as a result of this study are considered confidential and cannot be disclosed to a third party under any circumstances, except for cases mentioned below. Confidentiality will be ensured by the use of identification code.

Data generated as results of this study will be available upon request for review by investigators, representatives of the study sponsor, the scientific committee and the ethics committee (CPP).

## **8.6 COMPLETION OF STUDY**

The sponsor or [REDACTED] representative will notify the CPP, in writing, of the termination of the study.

## **8.7 SCIENTIFIC COMMITTEE**

No specific risks have been identified in the conduct of this routine clinical practice study where only the impact of additional nurse-led follow-up is evaluated. Thus, it can be considered that the risks to the patient participating in the study are negligible. Moreover, no treatment is administered blindly because treatments are administered as part of the routine practice of the medical team and no interim analysis will be performed. Therefore, it was decided not to establish an independent surveillance committee for this study.

A scientific committee was established for this study in order to participate in discussions on the study design, feasibility, implementation, monitoring, and analysis and interpretation of results.

